#### **7.2.7.2. Hypersensitivity Types 1 and 3 Reactions**

Type 1 hypersensitivity or allergic (eg, shortness of breath, urticaria, anaphylaxis, angioedema) reactions are theoretically possible in response to any injected protein. Immune complex mediated Type 3 hypersensitivity reactions are similar to the adverse events (AEs) of Type 1 reactions but are likely to be delayed from the time of injection and may include symptoms such as rash, urticaria, polyarthritis, myalgias, polysynovitis, fever, and, if severe, glomerulonephritis.

In the case of a hypersensitivity reaction, the subject will be treated symptomatically with supportive care, further monitoring, and treatment with anti-histamines and/or corticosteroids. Study injections may be stopped and the subject will be followed until the end of the study. At the time of any hypersensitivity reaction an ADA, PK, and PCSK9 specimen should be collected, and another sample collected at the next visit, as per the [Schedule of Activities](#).

If a subject reports an injection site reaction that has not resolved by the end of the third day, after dosing, an unscheduled visit should be performed, to collect an ADA, PK, and PCSK9 sample.

### **7.3. Health-Related Quality of Life and Depression Assessment**

#### **7.3.1. EQ-5D Health Questionnaire**

A health-related quality of life assessment, the EQ-5D Health Questionnaire, is administered at Visits 5 (baseline), 8, 9, 11, 14, 17, 20, and at early discontinuation from study or end of study visit ([Appendix 6](#)).

The EQ-5D is a generic measure of health-related quality of life. The EQ-5D is a subject completed instrument designed to assess impact on quality of life in five domains: mobility, self-care, usual activities, pain/discomfort, and anxiety/depression. Additionally, scores from the five domains may be used to calculate a single index value. The EuroQol EQ-5D Visual Analogue Scale (VAS) is a patient-completed 20 cm scale designed to rate an individual's current health state. The Health State Profile will be administered concurrently with the VAS-HEALTH STATE component of the EuroQol EQ-5D instrument.

The health outcomes assessment survey (EQ-5D) evaluates the subject's own perceptions. In order to gain the most objective results possible, subjects should complete the EQ-5D prior to performing any other study-related procedure for the visit and prior to any study-specific discussion of how they are feeling. The investigator must not influence the subject's assessments. Every effort should be made to maintain an unbiased assessment. All subject self-assessments should be reviewed for completeness while the subject is still present for the study visit.

#### **7.3.2. Patient Health Questionnaire Depression Module**

Depression is an affective disorder that sometimes occurs in patients with CV disease. The assessment of depression in patients with CV disease is recommended since it may impact the quality of life and adherence to medical treatment. The Patient Health Questionnaire (PHQ) depression assessment is a validated tool to assess the presence of depression and its severity. It will be used to evaluate subjects for clinical evidence of depression in this study.

The PHQ-2 consists of the first two items of the PHQ-9, and constitutes the two core DSM-IV items for major depressive disorder. The PHQ-2 score ranges from 0 to 6. The operating characteristics of this ultra-brief measure are quite good; the recommended cut-point when used as a screening test is a score of 3 or greater. This study will use a screening test score of 2 or greater, as a trigger for completion of the PHQ-9 assessment, as a

more conservative approach to identifying the presence of a major depressive disorder. The PHQ-2 provides depressive scores and can be used as a screening assessment for depression; the remaining 7 questions of the PHQ-9 evaluate the severity of depression. The severity is calculated by assigning scores of 0, 1, 2, and 3, to the response categories of “not at all”, “several days”, “more than half the days”, and “nearly every day”, respectively. PHQ-9 total score ranges from 0 to 27. Scores of 1-4, 5-9, 10-14, 15-19, and 20-27 represent minimal, mild, moderate, moderately severe, and severe depression, respectively.

The PHQ-2 will be performed in all subjects at Visit 5 (randomization), and in subjects with cognitive assessments only, it will be performed annually, and at EDC or EOS.

If at the baseline PHQ-2 assessment, a subject scores  $\geq 2$ , the remaining 7 questions of the PHQ-9 will be answered. If the PHQ-9 score is  $\geq 10$ , the subject should be referred back to his/her primary care physician for further assessment and/or treatment of potential major depression. If the PHQ-9 score is  $\geq 15$  or there is a positive score in question 9, the subject should be excluded from participation, the subject’s primary care physician (PCP) should be informed, and the subject should be referred to a mental health professional, either by the PCP or the investigator. Such subjects may be rescreened, at a later date, if they were evaluated and treated as appropriate, and the repeat PHQ scores permit inclusion. Any adverse events should be documented in the case report form as appropriate.

Only subjects participating in the cognitive assessment sub-study will have annual, and end of treatment or end of study PHQ assessments, in addition to the baseline assessment. If at any the visits after the baseline assessment, a subject scores  $\geq 2$ , the remaining 7 questions of the PHQ-9 will be answered. If the PHQ-9 score is  $\geq 10$ , consideration should be given to referring the subject back to his/her primary care physician for further assessment of potential major depression and recommendations. If the PHQ-9 score is  $\geq 15$  or there is a positive score in question 9, the subject’s primary care physician (PCP) should be informed, and the subject should be referred to a mental health professional, either by the PCP or the investigator. Any adverse events should be documented in the case report form as appropriate.

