		
data, and to enhance clarity for the investigators;
 
Modified study design to include a pre-screening direct low density lipoprotein cholesterol (LDL-C) measurement, to permit investigators to identify subjects who might qualify for inclusion, before other study procedures are completed;
 
Required that lipid assessments be done no sooner than 10 days after prior dose, to ensure that lipid values are evaluated at the end of the dosing period;
 
Added more frequent visits for assessment of direct LDL-C and adverse events (AEs)/serious adverse events (SAEs), for subjects who have had investigational product (IP) dose frequency modifications to Q4wks so that the data monitoring committee (DMC) can monitor more closely, lipid levels in subjects with a history of low levels of LDL-C during the trial;
 
Added endpoint of calculated remnant lipoprotein cholesterol, in consideration of scientific interest in this parameter;
 
Clarified that very low density lipoprotein cholesterol (VLDL-C) is a calculated value, so that reviewers understand the measurement was not made by ultracentrifugation;
 
Added depression assessments so as to capture baseline risk for the disorder, given that depression is found fairly frequently in subjects at high risk of cardiovascular events and its presence may alter performance on the planned cognitive assessments;
 
Added Hopkins Verbal Learning Testing to the cognitive assessment panel, to get additional information on the subjects' memory function;
 
Added health care utilization assessments and endpoints, to evaluate the potential impact of

Document	Version Date	Summary of Changes and Rationale

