Observed values and changes from baseline in hematology, blood chemistry, and quantitative urinalysis parameters will be tabulated by visit according to sponsor standards. Mean changes from baseline will be plotted longitudinally for selected laboratory parameters according to sponsor standards. Observations of potential clinical concern after the first dose of study medication for hematology, blood chemistry and all urinalysis parameters will be tabulated by treatment group according to sponsor standards. In addition, the number and percentage of subjects with positive ADAs and neutralizing ADAs will be tabulated for bococizumab-treated subjects.

12-lead ECGs will be locally read and the interpretations will be kept at the investigation sites as source documents. Any clinically significant ECG abnormalities will be reported as AEs.

Physical examination findings will be listed. Neurological exam findings will be summarized according to sponsor standards.

Changes from baseline in cognitive test results, including the Digit Span Forward score, Digit Span Backward Score, Digit Symbol - Coding score, Trail Making A score, Trail Making B score, HVLT Total Recall score, HVLT Delayed Recall Trial score, and the HVLT Recognition score, will be analyzed using an MMRM model. The fixed effects will be treatment group (categorical variable), scheduled visit time point (categorical variable), baseline value (continuous variable), interaction between treatment group and visit and interaction between treatment group and baseline value. Baseline value will be the last non-missing value on or before the day of randomization. REML estimation will be used and the default covariance structure will be unstructured. If the model fitting fails to converge, compound symmetry will be used as the covariance structure. Consistent with MMRM model fitting, no explicit imputation of missing assessments will be performed. Estimates of treatment group means and mean treatment group differences at each visit along with corresponding 95% confidence intervals will be provided. The confidence intervals are for estimation purposes only.

The PHQ-2 score and PHQ-9 score will be summarized by treatment group at baseline according to sponsor standards.

Time-to-event analyses of all-cause death will be repeated in the SAS. Adjudicated and confirmed causes of death will be tabulated by treatment group.

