6.4. Covariates

The randomization will be stratified by geographic region and complete statin intolerance. These variables will be included as stratification factors in log rank tests and Cox proportional hazards regression models and as covariates in linear models for efficacy endpoints. If the model fitting for the Cox proportional hazards model fails to converge, complete statin intolerance will be removed as a stratification factor.

Geographic region and complete statin intolerance will be obtained from the IRT system.

Complete statin intolerance is a binary variable. Subjects with complete statin intolerance will form one group; the other group will consist of subjects with partial or no statin intolerance.

The geographic regions (5 levels) are:

- USA/Canada: Canada, Puerto Rico, United States of America.
- Latin America: Argentina, Brazil, Chile, Columbia, Mexico, Peru.
- Eastern Europe/Turkey: Czech Republic, Hungary, Poland, Romania, Russia, Slovakia, Turkey.
- Asia: China, India, Japan, Korea, Taiwan, Thailand.
- Rest of World: Australia, Belgium, Denmark, Finland, France, Germany, Ireland, Israel, Italy, Netherlands, New Zealand, Republic of South Africa, Spain, Sweden, Switzerland, United Kingdom.

If a subject changes investigational sites during the study, geographic region will be assigned according to the site at which the subject was randomized.

For all linear models that involve changes from baseline, the baseline value will also be used as a covariate.

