Observations of potential clinical concern after the first dose of study medication for hematology, blood chemistry and all urinalysis parameters will be tabulated by treatment group as categorical variables according to sponsor standards. Subjects meeting one or more criterion for Hy's Law will be tabulated by treatment group according to sponsor standards.

The maximum post-randomization total bilirubin value will be plotted against the maximum post-randomization alanine transaminase (ALT) value (Evaluation of Drug-Induced Serious Hepatotoxicity [eDISH] plot).

Electrocardiograms

12-lead ECGs will be locally read and the interpretations will be kept at the investigation sites as source documents. Any clinically significant ECG abnormalities will be reported as AEs. As a result of the discontinuation of the bococizumab clinical development program, ECG data will not be summarized or listed.

Physical and neurological exams

As a result of the discontinuation of the bococizumab clinical development program, physical examination findings will not be listed. Also, neurological exam findings will not be summarized or listed.

Cognitive Tests

Changes from baseline in cognitive test results, including the Digit Span Forward score, Digit Span Backward Score, Digit Symbol - Coding score, Trail Making A score, Trail Making B score, HVLT Total Recall score, HVLT Delayed Recall Trial score, and the HVLT Recognition score will be analyzed using an MMRM model. The fixed effects will be treatment group (categorical variable), scheduled visit time point (categorical variable), baseline value (continuous variable), interaction between baseline value and scheduled visit time point and interaction between treatment and scheduled visit time point. REML estimation will be used and the default covariance structure will be unstructured. Due to the slow onset of accrual in this event-driven trial, there will be few observations at the last several time points. One or more of the last visits may be removed to ensure convergence of the model fitting. If the model fitting fails to converge, compound symmetry will be used as the covariance structure. Consistent with MMRM model fitting, no explicit imputation of missing assessments will be performed. Estimates of treatment group means and mean treatment group differences at each visit along with corresponding 95% confidence intervals will be provided. The confidence intervals are for estimation purposes only.

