Depression assessment

The PHQ-2 score and PHQ-9 score will be summarized by treatment group at baseline as categorical variables according to sponsor standards using the following categories: scores of 0, 1-4, 5-9, 10-14, 15-19, and 20-27, which represent no depression, minimal, mild, moderate, moderately severe, and severe depression, respectively.

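### The cognitive-test MMRM adjusts for no baseline variable except the test score; adding age, complete statin intolerance and (carefully) baseline PHQ-2 could narrow its intervals slightly

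*Protocol*

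**What the plan says.** - **PHQ schedule.** Protocol 7.3.2 requires the PHQ-2 in all subjects at Visit 5; after that, "in subjects with cognitive assessments only, it will be performed annually, and at EDC or EOS".
- **Why it was added.** The Amendment 1 entry in the Protocol's Document History gives the purpose as capturing baseline depression risk. It notes that depression is fairly frequent in this population and that "its presence may alter performance on the planned cognitive assessments".
- **Cognitive model.** SAP 8.2.3 states: "The fixed effects will be treatment group (categorical variable), scheduled visit time point (categorical variable), baseline value (continuous variable), interaction between baseline value" by visit, and treatment by visit. Protocol 9.4 lists the same main effects but different interactions, "interaction between treatment group and visit and interaction between treatment group and baseline value". Neither version contains age, PHQ, region or complete statin intolerance.
- **Planned use of the PHQ.** "The PHQ-2 score and PHQ-9 score will be summarized by treatment group at baseline as categorical variables" (SAP 8.2.3). No analysis of the repeated scores is planned.
- **Stratification.** "The randomization will be stratified by geographic region and complete statin intolerance" (SAP 6.4). The same section brings these factors in "as covariates in linear models for efficacy endpoints". Cognition is a safety endpoint (SAP 6.2).
- **Status of the results.** SAP 8.2.3 presents the cognitive confidence intervals for estimation only.

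**The concern.** SAP 8.1.1.2, directly after specifying the cognitive model, says that MMRM allows adjustment for important prognostic factors and that this increases precision. The model itself uses only one such factor. Age is collected, and Protocol 4.1 admits subjects from legal adulthood with no upper limit. Depression was named by the sponsor as something that could affect these tests.

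The comparison is a safety question in about 500 subjects, with 400 expected at Week 52 (Protocol 9.1.1). No hypothesis test is attached, so interval width is what the analysis delivers. Stratified randomization does not balance age or PHQ-2. With 200 per group, the standard error of a standardized baseline difference is sqrt(2/200) = 0.1, so a chance imbalance above 0.1 SD in one direction or the other has probability of about 32% for any one covariate. Adjusting for a prognostic baseline variable removes the effect of such an imbalance and reduces residual variance.

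**Working it through.** **Step 1: reproduce the plan's figures.** Inputs are in Protocol 9.1.1 and Table 3: 200 per group at Week 52, 175 at Week 104, SD 9 for Digit Symbol, SD 40 for Trail Making B, and precision defined as the 95% half-width. Formula for a difference of two means: 1.96 × SD × sqrt(2/n).

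- Digit Symbol, Week 52: 1.96 × 9 × sqrt(2/200) = 1.764 (Table 3: 1.76)
- Digit Symbol, Week 104: 1.96 × 9 × sqrt(2/175) = 1.886 (Table 3: 1.89)
- Trail Making B, Week 52: 1.96 × 40 × sqrt(2/200) = 7.84 (Table 3: 7.84)
- Trail Making B, Week 104: 1.96 × 40 × sqrt(2/175) = 8.38 (Table 3: 8.38)

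All 14 entries in Table 3 reproduce to two decimals.

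**Step 2: effect of extra baseline covariates.** Let R² be the partial R-squared of the added covariates given the baseline test score. The half-width is multiplied by sqrt(1 − R²), and the gain is worth 400/(1 − R²) − 400 additional tested subjects. The documents give no R²; 2% to 10% is assumed.

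| Assumed R² | Interval narrower by | Digit Symbol, Week 52 | Trail Making B, Week 52 | Equivalent extra subjects on 400 |
|---|---|---|---|---|
| 0 | – | 1.764 | 7.84 | – |
| 0.02 | 1.0% | 1.746 | 7.76 | 8 |
| 0.05 | 2.5% | 1.719 | 7.64 | 21 |
| 0.10 | 5.1% | 1.673 | 7.44 | 44 |

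The percentages are more reliable than the absolute widths. Table 3 does not say whether its SDs are already adjusted for the baseline score; if they are not, the absolute gains are overstated.

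**Step 3: the stratification factors.** Cognitive testing is confined to U.S. and Canadian sites (Protocol Schedule of Activities, footnote 6). These fall in a single region level (SAP 6.4), so region is constant in this subset and contributes nothing. For complete statin intolerance with prevalence p and mean shift d (in SD units), v = p(1 − p)d² and R² = v/(1 + v). Both inputs are assumed: p from 5% to 20% and d from 0.1 to 0.3.

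- Smallest: 0.05 × 0.95 × 0.01 = 0.000475, so R² = 0.0005 and the interval narrows by 0.02%.
- Largest: 0.20 × 0.80 × 0.09 = 0.0144, so R² = 0.0142 and the interval narrows by 0.7%.

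**Step 4: what missing PHQ-2 would cost.** If a fraction f of subjects is dropped for want of a baseline PHQ-2, the half-width is multiplied by sqrt((1 − R²)/(1 − f)). The gain is cancelled when f = R². For R² of 2% to 10%, that means losing 8 to 40 of 400 subjects.

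**The case against.** The strongest objection is that the obvious remedy could backfire. The PHQ arrived with Amendment 1, and SAP 1.2 says the matching SAP revision was begun while the study was running and after two DMC reviews had been held. Cognitive testing is older: SAP 1.2 describes the Hopkins test as an additional assessment and says existing cognitive summaries were replaced by MMRM. Subjects in the cognitive subset randomized before the PHQ was introduced would have no baseline score, and SAP 7 does not impute missing PHQ. A plain PHQ-2 covariate would drop them. They would be the earliest enrolled, and so would supply the late visits where SAP 8.2.3 already expects few observations. Their number is not given. This stands, and it governs how PHQ-2 may be used.

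It is also fair to say that:

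- the analysis is descriptive, with no margin, power claim or decision attached;
- the documents nowhere show that age or PHQ-2 predicts change once the baseline score is in the model;
- excluding subjects with PHQ-9 of 15 or more, or a positive question 9 (Protocol 4.2), narrows the PHQ range;
- even at the top of the assumed range the gain is about 0.09 points on Digit Symbol and 0.4 seconds on Trail Making B;
- the 400 subjects are a projection made before the program was discontinued.

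These points limit the size of the finding. They do not give a reason to leave out age, which costs nothing to include.

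**Conclusion.** The omission is real and its consequence is small: intervals about 1% to 5% wider than necessary if the added partial R² is 2% to 10%. That range is assumed. The baseline test score may already carry much of the age and depression signal, in which case the gain is at or below the lower end. Nearly all of any gain would come from age and PHQ-2.

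A reader might infer more, but the documents do not support the following:

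- **That the plan breaks its own rule on strata.** SAP 6.4 applies to linear models for efficacy endpoints, and these are safety endpoints.
- **That leaving out the strata costs much precision.** Region is constant in the subset, and statin intolerance is worth under 1% in every scenario tried.
- **That the repeated PHQ belongs in the model.** Those scores are post-randomization; conditioning on them could remove part of a treatment effect and would change what is estimated.
- **That the PHQ was added solely for the cognitive analysis.** The amendment log names baseline risk as well, and Protocol 7.3.2 cites quality of life and adherence.
- **That Table 3 is wrong.** It reproduces exactly.

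**What to change.** In SAP 8.1.1.2 and 8.2.3, add age (continuous) and complete statin intolerance (categorical) as fixed effects in the cognitive MMRM. State that statin intolerance is removed if the model does not converge, in line with the rule SAP 6.4 already has for the Cox model.

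Add baseline PHQ-2 only in a form that keeps every subject. Two options are a missing-value indicator and a single imputed baseline value, either one defined without reference to treatment or outcome. Each needs a stated exception to the no-imputation rule in SAP 7, limited to use as a covariate. Otherwise, keep PHQ-2 out of the main model and fit it as a sensitivity analysis. In no case use post-baseline PHQ.

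The cost is a few lines of SAP text and two or three model terms, settled before sponsor unblinding. No new data are needed. The number of cognitive-subset subjects without a baseline PHQ-2 should be counted on blinded data before choosing between the options.

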## **7.4. Pharmacokinetics**

### **7.4.1. Plasma for Analysis of Bococizumab and PCSK9**

Blood samples for bococizumab and PCSK9 will be collected as specified in the [Schedule of Activities](#). On all bococizumab/PCSK9 blood sample collection days, samples must be collected prior to bococizumab dosing. After randomization, if lipid sampling has been postponed to an unscheduled visit, the corresponding ADA, PK, and PCSK9 samples should be postponed as well, and collected at the at the same time as the rescheduled lipid sample collection. Bococizumab/PCSK9 blood samples will be collected from all subjects, but only analyzed, if needed, to help understand the PK, PD, and safety response of bococizumab in this study population. In addition, baseline PCSK9 samples collected on Visits 3 and 5 will be analyzed in a randomly selected subset of subjects (N=1,200).

Blood samples (4 mL) to provide a minimum of 1.5 mL of plasma for pharmacokinetic analysis will be collected into appropriately labeled tubes containing K2EDTA at times specified above.

Samples for bococizumab and PCSK9, if analyzed, will be measured using a validated analytical method in compliance with Pfizer standard operating procedures.

Detailed instructions for the preparation and shipment of the samples may be found in the Laboratory Manual supplied by the Central Laboratory.

As part of understanding the pharmacokinetics/pharmacodynamics of the IP, samples may be used for evaluation of the bioanalytical methods. These data will be used for internal (ie, Pfizer) exploratory purposes and will not be included in the clinical report.

